PROMIS Fatigue, FAACT, FACIT-D: Baseline (before Cycle 1 Day 1), end of Cycle 3, end of Cycle 6, end of Cycle 12, at end of protocol treatment, including treatment discontinuation for any reason (i.e., toxicity, progression, completion of protocol therapy) and 4 weeks after end of protocol treatment, including treatment discontinuation for any reason (i.e., toxicity, progression, completion of protocol therapy).

Rev. 10/16 The ECOG-ACRIN Medication Adherence Scale Modified from the Morisky Index: end of Cycle 3, end of Cycle 6, end of Cycle 12, and at  
Rev. Add7 end of protocol treatment, including treatment discontinuation for any reason (i.e. toxicity, progression, completion of protocol therapy).  
Please note there will be one Medication Adherence Scale form completed for each agent (entinostat/placebo and exemestane).

FACT-G: Baseline (before Cycle 1 Day 1), end of Cycle 3, end of Cycle 6, end of Cycle 12, and at end of protocol treatment, including treatment discontinuation for any reason (i.e. toxicity, progression, completion of protocol therapy).

8. The FBSI will be administered at baseline, end of each cycle for the first six months after randomization, and then at the end of Cycles 8, 10, and 12. After Cycle 12, the FBSI will be administered on the same schedule as Tumor assessments until disease progression.
9. Pill counts for entinostat/placebo and diaries for exemestane should be collected at the end of each cycle until discontinuation of study treatment.
10. Repeat any test not done  $\leq$  the prior 28 days.
11. Every 3 months if patient is  $< 2$  years from study entry, every 6 months if patient is 2-5 years from study entry, and annually if patient is  $>5$  years from study entry. No specific requirements if patient is more than 10 years from study entry.
12. Tumor assessments are to be done up to (and including) the assessment which shows first progression of disease. If patient discontinues treatment due to reasons other than disease progression, concomitant medication and tumor assessments should be performed until disease progression on the following schedule: Every 3 months if patient is  $< 2$  years from study entry, every 6 months if patient is 2-5 years from study entry, and annually if patient is  $>5$  years from study entry. No specific requirements if patient is more than 10 years from study entry.

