## 9.6 Patient-Reported Outcomes Assessment

There are two objectives in the patient-reported outcomes (PROs) assessment study. The first objective is to compare overall HRQL between treatment arms. The second objective is to compare symptoms associated with entinostat between arms. The type I error rate is equally split between the two objectives to control the overall one-sided type I error at 2.5% for the PROs analysis. In order to provide sufficient power for the two objectives, all 360 patients included for the PFS endpoint on the main study and receive at least one dose of protocol therapy (i.e., all treated patients) will be eligible for the PROs study. PROs will

not be evaluated on the additional 240 patients primarily enrolled for the OS endpoint.

Rev. Add7

With the exception of the FBSI and the Medication Adherence Scale, the PROs assessment will be administered at the following time points: baseline, 3, 6, and 12 months (the timing of these assessments coincides with the first, second and fourth disease assessments), at the end of protocol treatment/time of protocol treatment discontinuation and 4 weeks after protocol treatment is discontinued. Given that anticipated median survival is about 2 years and median PFS is about 4-7 months, the 3-month assessment is expected to provide the best assessment of treatment-emergent symptoms. Hence the primary comparison of PROs between treatment arms is based on the month 3 assessment.

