#### 9.6.1 Statistical consideration for PROs

The primary objective of the PROs study is to test whether the overall HRQL is significantly worse in the Exemestane + Entinostat arm (arm A) compared to the Exemestane + Placebo arm (arm B) at month 3. The null hypothesis is that patients on the two arms have same overall HRQL. The alternative hypothesis is that patients on arm A have worse HRQL than patients on arm B. The endpoint for the objective is the overall HRQL score measured by the Trial Outcome Index (TOI), an aggregate score of the 5 items from the FACT-G-Physical subscale (GP2, GP3, GP4, GP6, and GP7), and 6 items from the FACT-G-Functional subscale (GF1, GF2, GF3, GF4, GF6, and GF7). Higher score represents better HRQL (score range 0-44).

Assuming an overall attrition rate of approximately 10% by month 3 for the PROs assessment in both arms, it is expected that about 324 refractory patients will be included for the primary analysis for HRQL. At month 3, a difference of 5 points in the overall HRQL score between the treatment arms would be considered clinically meaningful. The common standard deviation is expected to be 12 points. With 162 analyzable patients on each arm for the month 3 assessment, there will be about 93% power to test the difference using a two independent samples t test, assuming a two-sided type I error of 0.025.

The second objective of the PROs study is to assess differences between the two arms in symptoms associated with entinostat at month 3 (i.e., fatigue, nausea, anorexia and diarrhea, measured by PROMIS Fatigue short form, FAACT-additional concerns and FACIT-Diarrhea, respectively). The null hypothesis is that there is no difference between two arms regarding fatigue, nausea, anorexia and diarrhea at 3-month assessment. The alternative hypothesis is that patients on the Exemestane + Entinostat arm have more severe symptoms than patients on the Exemestane + Placebo arm. For each of the four symptoms, with 162 analyzable patients on each arm in the study, there will be an adequate power (80%) to detect an effect size of 0.40 and an excellent power (90%) to detect an effect size of 0.45, using two independent samples t test, assuming a two-sided type I error of 0.00625 (=0.025/4). The effect size is the difference in the survey score between two arms divided by the population standard deviation for each symptom.

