#### 9.6.2 Analysis plan for PROs

The analysis time for PROs endpoints is at about 40 months (24 months of accrual + 12 months of treatment + 1 month follow up after treatment + 3 months of data collection and cleaning) after study activation. Subscale scores for all endpoints will be prorated by multiplying the sum of the subscale by the number of items in the subscale, then dividing by the number of items actually answered: Prorated subscale score = (sum of items cores) \* (number of items in subscale) / (number of items answered). When there are missing data, prorating by subscale in this way is acceptable as long as more than 50% of the items are answered in each subscale. For overall QOL, the FACT-G scale is considered to be an acceptable indicator of patient quality of life as long as overall item response rate is greater than 80%. For the four symptoms, the measurement scales (i.e., PROMIS-Fatigue, FAACT-Additional Concerns subscale, FACIT-Diarrhea) must be completed over 50% of the items (e.g., 4 of 7 items, 6 of 11 items and 7 of 12 items) in order to consider each subscale score valid.

Standard descriptive and graphical analyses will be used initially to examine missing data patterns, and to understand the relationship between variables. The assessment scores for the four symptoms and HRQL will be compared between the two treatment arms at baseline, month 3, month 6, month 12, at the end of protocol treatment and 4-week post-treatment (regardless of the reasons for off treatment), using two independent samples t test (or Wilcoxon rank sum test if the distribution of the score is not symmetric). Change in the four symptoms and HRQL between month 3 visit and the baseline visit will be compared between the two arms using two independent sample t tests. Similar analyses will be conducted for each FACT-G subscales as well. The mean score and proportion of moderate/severe symptoms will be compared between treatment arms for each individual FACT-G item at month 3 using Wilcoxon rank sum test and Fisher exact test, respectively, as an exploratory analysis.

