Mixed effect models will be constructed as another exploratory analysis to estimate the time profile of HRQL in the two treatment arms and to evaluate treatment-by-time interactions. Time will be included as a continuous variable if there is a linear trend in HRQL over time or a set of dummy variables if non-linear trend exists for HRQL. Likelihood ratio test will be used for model selection. Adjusted covariates included in the mixed effect models will include patient demographic and disease characteristics, such as age, ECOG PS, disease stage, prior therapy, et al.

As an exploratory analysis, patient-reported outcomes will be correlated with PFS (prognostic value of PROs) in the study patients. Patients will be dichotomized (e.g., by median) and/or categorized into groups (e.g, quantiles) based on their HRQL at baseline and 3-month assessment. Kaplan-Meier method, log rank test and Cox models will be used to compare PFS between patients with good QOL and those with poor QOL in the overall patient population. The predictive value of QOL for benefit from entinostat therapy will be examined via the QOL-by-treatment interaction test in a Cox model for PFS. Landmark method will be used when we correlate QOL at month 3 with PFS, and PFS will be defined as time from landmark time point to disease progression or death for these analyses.

In all analyses, P-values will be two-sided. A level of 2.5% will be considered statistically significant for QOL comparison between two arms. For the four symptoms, a level of 0.625% will be considered statistically significant for comparison between treatment arms. For all other analysis, a level of 5% will be considered statistically significant. No adjustment will be made for multiple comparisons for individual FACT-G items.

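### The primary month-3 PRO tests leave out the baseline score that the trial already collects; adjusting for it is a near-free gain in precision on secondary endpoints

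*Combined protocol and SAP*

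**What the plan says.** Section 9.6 fixes the time point: "Hence the primary comparison of PROs between treatment arms is based on the month 3 assessment". Section 9.6.1 powers the HRQL comparison (the Trial Outcome Index, built from FACT-G items) for a 5-point difference with SD 12, 162 analysable patients per arm and two-sided alpha 0.025: "there will be about 93% power to test the difference using a two independent samples t test". Each of the four symptoms is powered with the same test at two-sided alpha 0.00625, for 80% power at effect size 0.40 and 90% at 0.45. Section 9.6.2 repeats the two-sample t test and allows a Wilcoxon rank sum test "if the distribution of the score is not symmetric". No covariate is named for either test.

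Footnote 7 of the Section 7 calendar, in agreement with Section 5.6.3, shows that every scale involved has a pre-treatment measurement: "PROMIS Fatigue, FAACT, FACIT-D: Baseline (before Cycle 1 Day 1), end of Cycle 3" and "FACT-G: Baseline (before Cycle 1 Day 1), end of Cycle 3".

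Section 9.6.2 brings baseline into an arm comparison in two other places. One is a change-score test: "Change in the four symptoms and HRQL between month 3 visit and the baseline visit will be compared between the two arms". The other is exploratory and covers HRQL only: "Mixed effect models will be constructed as another exploratory analysis to estimate the time profile of HRQL in the two treatment arms". For those models, "Adjusted covariates included in the mixed effect models will include patient demographic and disease characteristics, such as age", ECOG PS, disease stage and prior therapy. The list is open-ended and does not name the baseline score.

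**The concern.** In a randomised comparison, a pre-treatment measurement of the same score usually explains part of the variation in the later score. Leaving it out leaves that variation in the error term and widens the confidence interval. Here the covariate is already collected for every score in the primary PRO comparisons, so the precision is available without extra patients, visits or forms.

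HRQL and entinostat-related symptoms are secondary objectives (2.2.5 and 2.2.6). The place where precision matters most is fatigue. Section 1.5 expects it to be the commonest side effect, and the lower end of its minimally important difference (effect size 0.40, Section 9.6.1) has only 80% planned power. For HRQL the alternative hypothesis is that the entinostat arm is worse, while Section 1.5 expects the arms to be comparable. A null result would be read through its confidence interval, so interval width matters even where power is already high.

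**Working it through.** **Inputs (Section 9.6.1).** n = 162 per arm (360 × 0.9 / 2). HRQL: difference 5, SD 12, two-sided alpha 0.025. Symptoms: effect sizes 0.40 and 0.45, two-sided alpha 0.00625. The correlation r between baseline and month-3 scores is not in the documents; a range of 0 to 0.7 is assumed.

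**Step 1: reproduce the plan.** Standard error = SD × √(2/n) = 12 × √(2/162) = 1.333. Noncentrality = 5 / 1.333 = 3.75 on 322 degrees of freedom. The noncentral t distribution gives:

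- HRQL: 93.2% (stated: about 93%).
- Symptoms at 0.40: 80.1% (stated: 80%).
- Symptoms at 0.45: 90.2% (stated: 90%).

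All three agree. The unadjusted 97.5% confidence interval half-width for HRQL is 2.252 × 1.333 = 3.00 points.

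**Step 2: add the baseline score as covariate.** Residual SD = SD × √(1 − r²), with one further degree of freedom used. For example, at r = 0.5 the residual SD is 12 × √0.75 = 10.39, the standard error is 1.155 and the noncentrality is 4.33.

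**Step 3: the planned change-score test.** SD of change = SD × √(2(1 − r)), assuming equal SDs at the two visits. This is below the raw SD only when 2(1 − r) < 1, that is, r > 0.5.

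| Assumed r | 0 | 0.2 | 0.3 | 0.5 | 0.7 |
|---|---|---|---|---|---|
| HRQL power, unadjusted | 93.2% | 93.2% | 93.2% | 93.2% | 93.2% |
| HRQL power, ANCOVA | 93.2% | 94.2% | 95.3% | 98.1% | 99.9% |
| HRQL power, change score | 65.5% | 76.2% | 82.0% | 93.2% | 99.5% |
| HRQL half-width, ANCOVA (points) | 3.00 | 2.94 | 2.86 | 2.60 | 2.14 |
| Symptom power at 0.40, unadjusted | 80.1% | 80.1% | 80.1% | 80.1% | 80.1% |
| Symptom power at 0.40, ANCOVA | 80.1% | 82.1% | 84.6% | 91.9% | 98.9% |
| Symptom power at 0.40, change score | 41.9% | 53.8% | 61.4% | 80.1% | 97.0% |

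**Step 4: where the gain falls.** The other symptom differences that the plan treats as important already have high unadjusted power: 95.9% at 0.50 (diarrhea), 97.8% at 0.53 (nausea/anorexia) and 99.8% at 0.63 (upper fatigue value). For those and for HRQL, adjustment mainly narrows the interval. For fatigue at 0.40 it also adds useful power when r is moderate.

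**The case against.** **No error is shown.** A two-sample t test is valid in a randomised trial, the stated powers are right, and Section 9.6.1 meets its own aim of at least adequate power for clinically important differences. All of this stands. The point is an improvement, not a repair.

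**The gain rests on an unknown correlation.** This also stands. A low r is plausible for some symptom scales: entry requires recovery of prior-treatment adverse events to grade 1 or baseline (3.1.17) and ECOG performance status 0–1 (3.1.20), which may narrow the baseline range, while month-3 nausea or diarrhea may be driven by study drug. At r of 0.2 the gain is one to two points of power. The answer is that the downside is negligible: at r = 0 the cost is one degree of freedom of 322.

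**Baseline is not ignored.** True. The change-score test covers HRQL and all four symptoms, Section 9.6.2 does not label it exploratory, and at r = 0.7 it comes close to ANCOVA. But it is not the powered comparison, and it is less powerful than the raw test whenever r is below 0.5. Baseline HRQL may also enter the mixed models as a repeated measure, but those models are exploratory and do not cover the symptom scores.

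**Stronger readings to avoid.** A reader might infer that everyone progressing before month 3 will give no month-3 form, so that true power is far below plan. The documents do not support deriving such a loss rate. The first scheduled scan is at 12 weeks (10.1.11), and Sections 5.6.3 and 9.6 say that it coincides with the month-3 assessment, so many such patients could still be on treatment and complete the form. A reader might also infer that dividing the symptom alpha by four is a mistake, because nausea and anorexia share one FAACT subscale. The plan names four symptoms, so the split is a defensible, conservative choice.

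**Conclusion.** The point holds as an efficiency improvement on secondary endpoints. Over assumed r from 0 to 0.7, ANCOVA moves HRQL power from 93% to between 93% and over 99%, and power at effect size 0.40 from 80% to between 80% and 99%. The HRQL interval half-width goes from 3.0 points to between 3.0 and 2.1. At a moderate r of 0.3 to 0.5, the gain at 0.40 is about 5 to 12 percentage points.

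These figures rest on the plan's 162 analysable patients per arm, its SD and effect sizes, a linear relation between baseline and month-3 scores, and an r that the documents do not supply. The arithmetic is secure; the realised gain is not known. Adjustment does not cure month-3 forms that are missing for reasons related to outcome, and it should not be presented as doing so.

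**What to change.** In Sections 9.6.1 and 9.6.2, define the primary month-3 PRO analysis as a linear model of the score on treatment arm and the same scale's baseline score. The randomisation stratification factors may be added. Before any unblinded PRO analysis, prespecify:

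- a simple rule for patients without a baseline form, for example mean imputation of the baseline covariate;
- a baseline-adjusted rank analysis, for example rank ANCOVA, for scores where the plan would use Wilcoxon.

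Keep the planned t test or Wilcoxon as supportive. The alpha allocation need not change.

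The cost is plan wording, with no new data, visits or patients. Because the study statistician has access to interim outcome analyses (9.2.1 and 9.9), the amendment should record that it was made without reference to unblinded PRO results.

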### 6.2.2 Treatment-related toxicities

PROs to assess fatigue and GI distress will be administered to measure treatment-related side effects.

6.2.2.1 PROMIS Fatigue: The PROMIS Fatigue is a 7-item short-form. Minimally important difference (MIDs) scores have been empirically derived for the PROMIS Fatigue short form^56 and use of the PROMIS fatigue short form will also allow us to compare this metastatic breast cancer sample to other cancers, non-cancer chronic illnesses, and general population norms. All items are rated on a 6-point Likert scale, from 0 to 5.

6.2.2.2 FAACT: The Functional Assessment of Anorexia/Cachexia Treatment (FAACT) subscale consists of 12 items focused on appetite and nausea. We will use the 12-item FAACT-additional concerns subscale to assess differences in nausea and anorexia. All items are rated on a 5-point Likert scale, from 0 to 4.

6.2.2.3 FACIT-Diarrhea: The 11-item Functional Assessment of Chronic Illness Therapy (FACIT)-Diarrhea subscale will be used to assess diarrhea. All items are rated on a 5-point Likert scale, from 0 to 4.

6.2.2.4 PRO-CTCAE: The NCI PRO-CTCAE library includes 78 items to quantify patient reports of AEs. We have selected 6 common treatment-related symptoms which will be measured using 13 PRO-CTCAE items: decreased appetite, diarrhea, nausea, vomiting, joint aches, and muscle aches. We have selected 2 additional symptoms (bruising, hiccups) that we anticipate to be similar between treatment arms for validation purposes. Hiccups will be measured using 2 PRO-CTCAE items.

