For the fatigue assessment, the clinically minimally important differences (MIDs) have been estimated for the PROMIS Fatigue short form in advanced-stage cancer patients, which is 3.0-5.0 points and corresponds to effect sizes between 0.4 and 0.63. For the nausea/anorexia assessment, the clinically minimally important difference is estimated to be 6 points using the FAACT-additional concerns subscale, corresponding to an effect size of 0.53. For the diarrhea assessment, we are planning to use the FACIT-Diarrhea subscale, which does not yet have published MIDs. We propose using 1/2 of the standard deviation of the FACIT-D scores (this is comparable to an effect size of 0.5) along with a general estimate of 0.36 points per item. Since the FACIT-D has 11 items, the estimated MID would be 4 points. Overall, this study should have an at least adequate power to detect a clinically important difference in each of the four symptoms, controlling the overall type I error rate at 2.5% for the second objective.

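### The second PRO objective divides its alpha by four symptoms, but the plan defines only three scores, so a quarter of that alpha goes unused

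*Combined protocol and SAP*

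**What the plan says.** Secondary objective 2.2.6 and the second PRO objective in Section 9.6.1 name four symptoms. Section 9.6.1 links them to their instruments in one phrase: "fatigue, nausea, anorexia and diarrhea, measured by PROMIS Fatigue short form, FAACT-additional concerns and FACIT-Diarrhea, respectively". That is four symptoms and three instruments.

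The significance level follows the count of symptoms. Section 9.6.1 divides 0.025 by four to give two-sided 0.00625 and states power on that basis: "For each of the four symptoms, with 162 analyzable patients on each arm in the study", 80% at an effect size of 0.40 and 90% at 0.45. Section 9.6.2 repeats the threshold: "For the four symptoms, a level of 0.625% will be considered statistically significant for comparison between treatment arms".

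The measurement follows the count of instruments. Section 6.2.2.2 says "We will use the 12-item FAACT-additional concerns subscale to assess differences in nausea and anorexia". Section 9.6.1 gives one minimally important difference (MID) for the pair: "For the nausea/anorexia assessment, the clinically minimally important difference is estimated to be 6 points using the FAACT-additional concerns subscale". It attaches a single standardized value, 0.53, to that difference. Section 9.6.2 gives completeness rules for three scales only: "For the four symptoms, the measurement scales (i.e., PROMIS-Fatigue, FAACT-Additional Concerns subscale, FACIT-Diarrhea) must be completed over 50% of the items". No section splits the FAACT subscale into a nausea score and an anorexia score.

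**The concern.** A Bonferroni divisor should equal the number of distinct hypotheses that the data can test. Here the divisor is four and the number of scores is three. Section 9.6.1 also defines the effect size through a standard deviation for each symptom, yet three scores supply only three standard deviations.

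Two things are at stake. The first is what may be claimed. A FAACT difference supports a statement about nausea and anorexia jointly and cannot show which of the two produced it. The two could move apart: Section 5.5.5 provides for prophylactic antiemetics, and Section 5.5 lists no counterpart for appetite. Section 1.5 intends the PRO results to inform patient counseling, so readers need to know exactly what was tested.

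The second is efficiency. The threshold for every symptom score is stricter than the objective's error budget requires. That includes fatigue, which Section 1.5 expects to be the most common side effect.

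**Working it through.** **Inputs.** All come from Sections 9.6 and 9.6.1.
- Alpha: the one-sided 2.5% for the PRO study is split equally between two objectives. Each gets 1.25% one-sided, which is 2.5% two-sided.
- Sample: 360 × 0.9 = 324 patients, or n = 162 per arm.
- Test: two independent samples t test.
- Effect sizes at the MIDs: fatigue 0.4 to 0.63, nausea/anorexia 0.53, diarrhea about 0.5.

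**Step 1: reproduce the stated power.** By the normal approximation, power = Φ(d·√(n/2) − z), where z is the two-sided critical value and √(162/2) = 9. At alpha 0.00625, z = 2.734.
- d = 0.40: Φ(3.60 − 2.734) = Φ(0.866) = 80.7% (noncentral t: 80.1%)
- d = 0.45: Φ(4.05 − 2.734) = Φ(1.316) = 90.6% (noncentral t: 90.2%)

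The plan's 80% and 90% are confirmed.

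**Step 2: count the alpha used.**
- Four tests: 4 × 0.00625 = 0.025
- Three distinct scores: 3 × 0.00625 = 0.01875
- Unused: 0.025 − 0.01875 = 0.00625, a quarter of the objective's allocation

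If the FAACT score were formally tested twice, the second test would give the same result as the first and add no false positives. The familywise bound therefore remains 0.01875, below 0.025.

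**Step 3: divide by three.** 0.025/3 = 0.00833, with z = 2.638. Power by the noncentral t with 162 per arm:

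| Effect size | Alpha 0.00625 | Alpha 0.00833 | Gain (points) |
|---|---|---|---|
| 0.40 | 80.1% | 82.7% | 2.6 |
| 0.45 | 90.2% | 91.8% | 1.6 |
| 0.50 | 95.9% | 96.7% | 0.8 |
| 0.53 | 97.8% | 98.2% | 0.5 |

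By the normal approximation, the detectable effect size falls from 0.397 to 0.387 at 80% power and from 0.446 to 0.436 at 90% power.

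**Sensitivity to n.** Section 9.3.3 assumes 171 treated patients per arm. With 10% attrition from that number (171 × 0.9 ≈ 154), power at 0.40 goes from 77.5% to 80.3%. The gain is similar.

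**The case against.** The strongest reply is that the plan is merely conservative. Error control at 2.5% for the second objective holds, as Section 9.6.1 claims. Power at the FAACT and diarrhea MIDs is above 95% under either divisor, and the statement of at least adequate power survives. No sample size or data collection depends on the choice, and the objective is secondary. All of this stands, and it keeps the point small.

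Three stronger readings are tempting, and the documents support none of them.
- *Type I error is inflated, or actively spent on a duplicate test.* It is not. The surplus alpha is simply left unused.
- *One FAACT result will be reported as two findings.* No section says so. Section 9.6.1 already speaks of a single nausea/anorexia assessment with one MID. The four-symptom wording leaves room for such reporting but does not plan it.
- *The trial can say nothing about nausea and appetite separately.* This is too broad. Section 6.2.1 selects individual FACT-G items, including nausea, and Section 9.6.2 compares the individual items between arms as an exploratory, unadjusted analysis. Section 6.2.2.4 lists nausea and decreased appetite as separate PRO-CTCAE symptoms, under exploratory objective 2.3.2. The limit applies only to the formal, alpha-controlled comparison.

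The reply leaves one thing unanswered: the objective and both alpha statements count four symptoms, while the scoring rules and MIDs support three tests.

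**Conclusion.** The concern holds as a mismatch between hypotheses and scores. The divisor of four is too large for three scores, and 0.00625 of the 0.025 goes unused. The cost is about 2.6 points of power at effect size 0.40, 1.6 points at 0.45, and under 1 point at 0.50 to 0.53. No alpha-controlled conclusion on nausea or on anorexia separately is possible. False-positive control and the plan's power arithmetic are both sound, and PFS and OS are untouched.

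These figures assume the plan's 162 patients per arm, its t test, an equal Bonferroni split, and a single FAACT score as the only formal measure of nausea and anorexia.

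**What to change.** In Sections 9.6.1 and 9.6.2:
- Define the second objective as three scale-score tests (PROMIS Fatigue, FAACT-additional concerns, FACIT-Diarrhea), each at two-sided 0.025/3 = 0.00833.
- Restate power as about 83% at effect size 0.40 and 92% at 0.45.
- Label the FAACT result as combined nausea/anorexia throughout, and align the wording of objective 2.2.6.
- State that separate results are descriptive: nausea from the FACT-G and PRO-CTCAE items, appetite from the PRO-CTCAE items. Section 9.6.2 does not yet describe a between-arm summary of the PRO-CTCAE items, so one sentence is needed.

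Because this loosens a stated threshold, it must be fixed before any unblinded PRO data are seen.

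The change is to wording only and needs no new data. The downside is that separate claims about nausea and anorexia become explicitly descriptive. If four formal tests are wanted instead, 0.025/4 can stay, but distinct nausea and anorexia scores, each with its own MID, would have to be prespecified from items already collected.
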